#### 5 SUBJECT SELECTION AND WITHDRAWAL

### 5.1 Number of Subjects

A minimum of 22 completed subjects will be needed for the study with enrollment of a maximum of 100 subjects.

#### 5.2 Inclusion Criteria

- Age greater than 18 years
- ASA physical status III or IV
- Scheduled for an elective surgical procedure requiring endotracheal intubation and the use of an arterial pressure monitoring catheter placed prior to induction of general anesthesia

### 5.3 Exclusion Criteria

- Age less than 18 years
- Adults unable to give primary consent
- Pregnancy
- Prisoners

# 5.4 Study Timelines

- This study is anticipated to require up to 3 months for completion of patient enrollment.
- Primary analysis of the data is expected to require an additional 6 months.

#### 5.5 Subject Recruitment and Screening

Patient recruitment and informed consent will be obtained in the UCDMC perioperative suite. Recruitment will be by direct discussion between the prospective candidates and the study investigators prior to their scheduled surgical procedure. The investigators will provide the consent form in person and give the prospective subject sufficient time to review the consent form and discuss the study with friends and family.

All items of the Informed Consent will be explained in a way that is easily understandable. The patient will be given adequate time to read through the Informed Consent, and they will be given adequate time and privacy to consider the decision of whether or not to sign the Informed Consent Form. Once all of the patient's questions have been answered and the Informed Consent Form signed, the patient is now adequately consented. Now the patient will be enrolled as a study subject, at which time the subject will be assigned a study identification number or enrollment number.

All subjects will have their medical history reviewed at the time of screening by either the PI or the study staff who is delegated for this task. Subjects will be evaluated based on the inclusion and exclusion criteria to determine eligibility to be enrolled into the study. If a subject is deemed ineligible after screening, the subject will be withdrawn from the study.

Information regarding the subject's demographic (including, but not limited to age, weight, race, ethnicity, etc.), preexisting allergies, skin abnormalities, and other preexisting diseases/conditions that may be relevant to the study will be recorded within a paper-based Case Report Form (CRF).

#### **HIPAA**

The screening of patients will require the investigators to access personal health information to identify prospective subjects without HIPAA authorization. The research could not be practicably carried out without this waiver of consent. The risk of harm from contacting the participants is greater than the risk of the study procedures. The research is of minimal risk and does not involve any procedures for which written consent is normally required outside the research setting. The participants' rights and welfare will not be adversely affected by waiving consent. This protected health information will not be inappropriately reused or disclosed to any other person or entity. To further safeguard all protected health information, the data will not be labeled with any personal identifying information, or with a code that this research team can link to personal identifying information. The data will not be stored with any protected health information identifiers.

#### 5.6 Early Withdrawal of Subjects

#### 5.6.1 Withdrawal of Individual Subjects

Subjects can leave the study at any time for any reason if they wish to do so without any consequences or loss of benefits to which they are otherwise entitled. Subjects may be withdrawn from the study prior to expected completion for reasons such as safety concerns, failure to adhere to protocol requirements, subject consent withdrawal, etc.

Any data collected until the time of subject withdrawal may be included in the final data analysis. Information on the subject's withdrawal should be documented in the case report form and should include clear documentation of the reason for withdrawal to the Sponsor.

5.6.2 Follow-up for subjects withdrawn from study

None. There are no long term effects anticipated from participating in this study.

5.6.3 Data from individual subjects after withdrawal

In case a subject leaves the study prematurely, the data collected may be included in data analysis.

#### 6 STUDY DEVICE

#### 6.1 **Study Device**

The Masimo Radical-7 is a noninvasive monitor that measures arterial oxygen saturation (SpO2), pulse rate (PR), and perfusion index (PI), along with optional measurements of hemoglobin (SpHb), carboxyhemoglobin (SpCO®), total oxygen

content (SpOC), methemoglobin (SpMet), Pleth Variability Index (PVI®), Oxygen Reserve Index (ORI™), Acoustic Respiration Rate (RRa®), and Pleth Respiration Rate (RRp). Masimo SET® technology is clinically proven to satisfy all sensitivity and specificity requirements for pulse oximetry. Masimo rainbow® technology uses 7+ wavelengths of light to continuously and noninvasively measure carboxyhemoglobin (SpCO), methemoglobin (SpMet), and total hemoglobin (SpHb®), as well as providing a more reliable probe-off detection. Total oxygen content (SpOC) provides a calculated measurement of the amount of oxygen in arterial blood, which may provide useful information about oxygen both dissolved in plasma and combined with hemoglobin. Perfusion Index (PI) with trending capability indicates arterial pulse signal strength and may be used as a diagnostic tool during low perfusion. Pleth Variability Index (PVI) may show changes that reflect physiologic factors such as vascular tone, circulating blood volume, and intrathoracic pressure excursions. [The utility of PVI is unknown at this time and requires further clinical studies. Technical factors that may affect PVI include probe malposition and patient motion.] Oxygen Reserve Index (ORI) is an index measured noninvasively and continuously to provide an earlier indication of impending hypoxia by extending oxygen monitoring of pulse-oximetry to the moderate hyperoxic regions. Respiration rate can be determined by the acoustic (RRa) or plethysmographic waveform (RRp). Signal IQ is a feature for signal identification and quality indication during excessive motion and low signal to noise situations. FastSat® tracks rapid changes in arterial O2. A detailed description of the Masimo Radical-7 can be found in the attached manual.

The Masimo Root System is also being used in this study. The Root System is indicated for use by healthcare professionals for the monitoring of multiple physiological parameters in healthcare environments. The Root works together with the Radical-7 to display data. The Root serves as a convenient alternative user interface to integrate modules to provide health care professionals the ability to access, control and monitor measurement technologies (within the respective modules) that have been previously cleared by the FDA.

Rainbow Adhesive Sensors are FDA cleared for the measurement of functional oxygen saturation of arterial hemoglobin (SpO2), pulse rate (PR), perfusion index (PI), pleth variability index (PVI), carboxyhemoglobin saturation (SpCO), methemoglobin saturation (SpMet), total hemoglobin (SpHb) and total oxygen content (SpOC). Although no modifications are required for the Rainbow Adhesive sensors for the study, the sensors have not been cleared for the indications for use of measuring ORi.

### 6.2 Risk/Benefits

Benefits: There is no specific benefit to the individual subjects for participation in this research protocol.

**Sensor risks:** As with all optical sensors, the investigational device has the risk of thermal burn. Pulse CO-oximeter noninvasive measurement uses wavelengths in the red and near infrared range like a conventional pulse oximeter used in routine clinical practice for over 15 years. The additional LEDs from Rainbow sensors have been tested and meet the Exempt classification for photo-biological safety of light sources.

All patient-contact materials, including the adhesive used in the design of the Masimo Rainbow sensors, have been subjected to biocompatibility tests per ISO 10993-1 and results demonstrate that the materials are non-toxic, non-irritating, and non-sensitizing. The sensors have been subjected to performance, mechanical, and electrical testing and results demonstrate that the sensors meet the requirements for safety and effectiveness for the intended use of the product.

No other physical, financial, social or psychological risks are anticipated to be associated with participation in this study as it only observation with the recording of intraoperative ORI and ABG measurements. Precautions taken to safeguard protected personal health information are described in the section on recruitment. The risks associated with the anesthetic and surgical procedure are not discussed in this proposal.

# 6.3 Device Accountability

# 6.3.1 Receipt of Study Device

Upon receipt of the of the study device supplies, an inventory must be performed and the device accountability log filled out and signed by the person accepting the shipment. It is important that the designated study staff counts and verifies that the shipment contains all the items noted in the shipment inventory. Any damaged or unusable study devices in a given shipment will be documented in the study files. The investigator must notify the study sponsor of any damaged or unusable study devices that were supplied to the investigator's site.

### 6.3.2 Use of Study Device

Use of devices and sensors will be documented on case report forms for each subject. Any unused devices must be returned to the Sponsor at the end of the study or before product expiration date.

# 6.3.3 Return or Destruction of Study Device

At the completion of the study, there will be a final reconciliation of study devices and sensors shipped, devices/sensors used, and devices/sensors remaining. This reconciliation will be logged on the device accountability log. Any discrepancies noted will be investigated, resolved, and documented prior to return or destruction of unused study devices. Devices destroyed on site will only be upon written instruction from the sponsor and will be documented in the study files.

[figure not shown]
#### 6.3.4 Device Deficiencies

Device deficiencies are defined as the inadequacy of a medical device with respect to its identity, quality, durability, reliability, safety or performance. Record all device deficiencies on the case report form and report to the Sponsor.

### 7 STUDY PROCEDURES

- 7.1 Following arrival of the patient in the operating room all standard and planned physiological monitors will be placed. A baseline ORi will be measured and an arterial blood gas (ABG) sample will be collected for measurement of the PaO2.
- 7.2 As per routine, the patient will then be pre-oxygenated with 100% oxygen. a second ORI will be recorded and ABG sample collected.
- 7.3 General anesthesia will be induced with a combination of amnestics, narcotics, intravenous induction agents and muscle relaxants as clinically indicated. With stable mask ventilation, a third ORI will be recorded and ABG sample collected immediately prior to initiating laryngoscopy and endotracheal intubation.
- 7.4 Intubation will be under direct visualization using a GlideScope. When the arterial hemoglobin saturation reaches fourth ORi will be recorded, an ABG sample will be collected and ventilation will be initiated with 100% oxygen either via the endotracheal tube or resumed mask ventilation.
- 7.5 A final post-induction ORi measurement and ABG sampling will occur 5 minutes following initiation of controlled ventilation with 100% oxygen.

This planned protocol sequence can be summarized graphically as:

Arterial blood gas measurement: ABG samples will be analyzed using Radiometer's ABL blood gas analysis system. Each sample will use of blood for a total blood volume of for this study.

#### 8 STATISTICAL PLAN

### 8.1 Sample Size

The same sample size calculation used for the healthy subjects is used to determine the sample size for this study with sick subjects, which is calculated to be a minimum of 22 subjects. Based on this, the sample size for the study with sick subjects is established as the following for 95% confidence interval:

Number of Subjects	Number of Invasive Measurements per Subject	Number of Noninvasive Sensors Per Subject
22 minimum 	4 minimum	1 minimum

# 8.2 Acceptance criteria

In accordance with ISO-80601-2-61, SpO2 accuracy is determined as accuracy root mean square (ARMS), where SpO2 measurements are compared with reference SaO2 measurements. However unlike SpO2, ORi is an index value without a unit and ORi does not directly measure PaO2. Therefore, sensitivity and specificity analysis is used to evaluate ORI's performance relative to the changes in PaO2.

Although concordance calculation is based on sensitivity and specificity analysis, concordance analysis is not applicable for the sick subjects because of the lack of sample size. Thus the specifications for ORI are the following:

- Specificity of ΔPaO2 vs. ΔORI > 80%
- Sensitivity of  $\triangle PaO2$  vs.  $\triangle ORI > 85\%$
- Concordance of ΔPaO2 vs. ΔORI > 80%

Where  $\Delta$ PaO2 is the change in PaO2 and  $\Delta$ ORi is the change in ORi. These specifications are based on the study by Applegate et al. The Applegate study evaluated the ORI to PaO2 relationship during surgery of 106 patients. The data showed that decreasing ORI had 77.7% sensitivity and 76.7% specificity for detecting decreasing PaO2.

In determining specificity and sensitivity,  $\Delta PaO_2$  and  $\Delta ORi$  are defined as:

$$\Delta PaO_2 = PaO_2(t) - PaO_2(t_{ref})$$

$$\Delta ORI = ORI(t) - ORI(t_{ref})$$

Where  $t_{ref}$  is the time of the sample closest to  $PaO_{2threshold}$  in a mmHg window. Thus, a mmHg window is used as it is not possible to draw a blood sample at the exact value of  $PaO_{2threshold}$ .

Samples with  $\triangle$  PaO2 of mmHg are ignored.

# 8.3 Statistical analysis

Similar statistical analysis as described in the study with healthy subjects ( will be performed on the data for this study with sick subjects. However unlike healthy subjects, the FiO2 levels for sick subjects cannot be easily varied. Therefore, substantially fewer PaO2 samples are available for sick subjects. As a result, all PaO2 samples for sick subjects are accounted for in data analysis even if the PaO2 sample is outside the 100 to 200 mmHg range.

[figure not shown]

Figure 3: Specificity and Sensitivity Illustration for ΔPaO2 vs ΔORi

In accordance with Figure 3, the following relationships are defined as:

Specificity =  $\frac{N1}{(N1 + N4)}$ , where  $t_{ref}$  is the baseline sample time

Sensitivity =  $\frac{N3}{(N2 + N3)}$ , where  $t_{ref}$  is the sample time at the end of 100% pre-oxygenation.

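### Section 8.3 takes specificity from the pre-oxygen baseline and sensitivity from the end of pre-oxygenation; on the standard quadrant reading, the pair cannot support a statement about false warnings.

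*Combined protocol and SAP*

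**What the plan says.** Section 8.3 defines specificity as N1/(N1+N4), where t_ref "is the baseline sample time", and sensitivity as N3/(N2+N3), where t_ref "is the sample time at the end of 100% pre-oxygenation". The quadrants are shown in Figure 3, which the available text does not reproduce.

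Section 7 fixes the order of sampling. At 7.1, "A baseline ORi will be measured and an arterial blood gas (ABG) sample will be collected"; 100% oxygen follows at 7.2, with a second ORi and blood gas. The third pair is taken under mask ventilation just before laryngoscopy (7.3) and the fourth at a set saturation (7.4). At 7.5, "A final post-induction ORi measurement and ABG sampling will occur 5 minutes following initiation of controlled ventilation with 100% oxygen".

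Section 8.2 has a single t_ref for both rates, which "is the time of the sample closest to" a PaO2 threshold. Samples whose PaO2 change lies in a redacted range of "mmHg are ignored". The limits are above 80% for specificity and above 85% for sensitivity. They are said to rest on a cited study in which "decreasing ORI had 77.7% sensitivity and 76.7% specificity for detecting decreasing PaO2".

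Section 8.3 adds that "all PaO2 samples for sick subjects are accounted for in data analysis even if the PaO2 sample is outside the 100 to 200 mmHg" range. It does not list which samples enter which rate.

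Early warning of desaturation is a specific aim (2.1) and the secondary endpoint (3.1).

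**The concern.** Sensitivity and specificity describe one test against one event: how often the test is positive when the event occurs, and negative when it does not. Here the sensitivity event is a PaO2 fall from the value reached on oxygen. The matching specificity would use samples whose PaO2 has not fallen from that same value. The plan uses samples whose PaO2 has risen from the pre-oxygen value instead.

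An early-warning claim depends on how often ORi drops when PaO2 does not. If the planned specificity cannot register such drops, a result above 80% says nothing about them, although the word specificity invites that reading.

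**Working it through.** **Inputs from the documents.** The two formulas and their reference times (8.3), the order of the five samples (7.1 to 7.5), the limits (8.2), and the minimum of 22 subjects (5.1, 8.1). The plan gives no expected value for either rate under its definitions, so there is no planned figure to reproduce.

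**Assumptions.** PaO2 is the reference. N1 is PaO2 up and ORi up; N4 is PaO2 up and ORi not up; N3 is PaO2 down and ORi down; N2 is PaO2 down and ORi not down. All PaO2 and ORi values below are assumed, because the documents give none.

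**Step 1: logic.** Take a sample after pre-oxygenation where PaO2 has not fallen from its pre-oxygenation value, ORi has fallen, and both remain above baseline.
- Sensitivity: there is no PaO2 fall, so the sample is outside N2+N3 and is not counted.
- Specificity: both changes from baseline are positive, so it enters N1 as correct. If only the pre-oxygenation sample enters this rate, it is not assessed.

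It can enter N4 only if ORi drops to or below its baseline value.

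**Step 2: the mask-ventilation sample.** Assume PaO2 80, 150, 190 mmHg and ORi 0.00, 0.60, 0.30 at baseline, end of pre-oxygenation and mask ventilation.
- From the end of pre-oxygenation: PaO2 190 - 150 = +40; ORi 0.30 - 0.60 = -0.30. This is a fall in ORi without a fall in PaO2.
- From baseline: PaO2 190 - 80 = +110; ORi 0.30 - 0.00 = +0.30. Scored N1, correct.

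If a share f of same-reference non-falls behave this way, the same-reference specificity is 1 - f. The planned figure does not move with f while ORi stays above baseline.

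**Step 3: all five samples, 22 identical subjects.** Assume PaO2 80/150/130/60/190 mmHg and ORi 0.00/0.60/0.45/0.05/0.30.

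| Rate | Reference | Pairs per subject | Result |
|---|---|---|---|
| Sensitivity, as planned | End of pre-oxygenation | PaO2 -20 and -90; ORi -0.15 and -0.55 | 44/44 |
| Specificity, as planned | Baseline | PaO2 +70, +50, +110; ORi +0.60, +0.45, +0.30 | 66/66 (22/22 if only the pre-oxygenation sample enters) |
| Specificity, same reference as sensitivity | End of pre-oxygenation | PaO2 +40; ORi -0.30 | 0/22 (Wilson 95% interval 0% to 15%) |

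If m of the 22 subjects show that last pattern and the others rise, the planned figure stays 66/66 and the same-reference figure is (22 - m)/22. At m = 5 it is 17/22 = 77.3%.

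Every pair in the last row comes from the 5-minute sample. That sample follows desaturation and renewed ventilation, and over the last interval ORi was climbing from 0.05 to 0.30 as PaO2 went from 60 to 190. The row therefore reflects incomplete ORi recovery. At the mask-ventilation sample in this profile, PaO2 and ORi fall together.

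**Step 4: the redacted cut-off.** Let c be the PaO2 change up to which pairs are ignored. For c below 20 mmHg the counts are as shown. For c from 20 to below 40, sensitivity becomes 22/22 and the rest is unchanged. From c = 40 the same-reference pairs drop out (0/0).

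**Step 5: where the planned specificity does react.** An index that falls from baseline at all three risen samples scores 0/66. If the desaturation PaO2 is above baseline (65 against 60) with ORi exactly back at baseline, and ties count as N4, the planned figure is 66/88 = 75% and fails (for c below 5).

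**The case against.** **The pair may be a deliberate tracking check.** Section 8.2 says the rates assess ORi against changes in PaO2, which suits the primary endpoint, and the limits are not tied to the early-warning endpoint. Section 8.3 notes that FiO2 cannot easily be varied and samples are few, so each direction is measured where it is expected. This stands, and is why the planned ratio should be kept. It does not supply a false-warning figure.

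**Figure 3 is missing.** With the axes swapped, the two ratios would be predictive values and N2 would count false ORi falls from the end of pre-oxygenation. The scoring argument would then fail. The labels favour the usual reading, and the reference times would differ either way, but the point has to be conditional.

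**Stronger readings that the documents do not support.**
- A reader might take 0/22, or 17/22, as a rate of false early warnings. It is not: those pairs postdate the desaturation.
- A reader might infer that the cited 76.7% is a different quantity from the planned specificity. The documents do not give that study's reference time, so this cannot be settled. Nor do they plan a comparison with 76.7%; they only base the limits on that study.
- A reader might infer that an uninformative index would pass. In 20,000 simulated studies of 22 subjects per setting (ORi uniform 0 to 1 on oxygen, 0.00 at desaturation, baseline ORi 0.00 to 0.15), both limits were met in about 2% to 6%, because mean sensitivity was 75%.

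**The added figure may rest on little.** Section 8.1 requires only four invasive measurements per subject, and the cut-off is redacted. This stands, and is counted as a cost below.

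**Conclusion.** The concern holds in conditional form. That three reference times appear, two in 8.3 and one in 8.2, is on the page and needs no assumption. On the usual quadrant reading, the planned specificity is the detection rate for PaO2 rises from the pre-oxygen baseline. It is blind to ORi falls after pre-oxygenation without a PaO2 fall while ORi stays above baseline. The planned pair therefore cannot support a statement about false warnings for the secondary endpoint.

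The size in practice is unknown. Under assumed values the two references can differ as far as 66/66 against 0/22, which shows that they can disagree, not how often ORi would mislead before laryngoscopy. The change should be made; the analysis can run as written, but its specificity should not be read as a false-warning rate.

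**What to change.** In section 8.3:

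1. Add specificity for falls from the end of pre-oxygenation, over later samples whose PaO2 did not fall, with a confidence interval. Report the mask-ventilation sample separately from the 5-minute sample, and base any false-warning statement on the mask-ventilation figure.
2. Keep the baseline-referenced N1/(N1+N4), labelled as detection of PaO2 rises. State in 8.2 which figure the >80% limit applies to.
3. Reconcile t_ref between 8.2 and 8.3, and list which samples enter each rate.

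Cost: SAP wording only, since section 7 already schedules the samples. The added figure will be imprecise: with 22 subjects there are at most 22 pairs per time point, possibly none after the redacted cut-off. For scale, 18/22 = 82% has a Wilson 95% interval of about 61% to 93%. It may also be less favourable than the planned figure.

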# OxyHemoglobin Dissociation Curve

[figure not shown]

Figure 1: The oxygen dissociation curve with the three oxygen states

In order to prevent episodes of hypoxia, patients in critical care are administered a certain amount of supplemental oxygen to prevent hypoxia and improve safety in situations where the oxygen supply may be lost intermittently. However this excess supply should be in moderation as large amounts of oxygen may result in lung damage or other complications. Hence it becomes imperative to monitor the amount of surplus oxygen in blood.

Currently, clinicians monitor a patient's oxygen status, both continuously and non-invasively, using a pulse oximeter to obtain SpO2 (a proxy for SaO2) levels. However, SpO2 is sensitive in the normoxic and hypoxic regions and largely remains flat in the hyperoxic region (Figure 1). Clinicians consequently must resort to invasive blood sampling to obtain PaO2 values for oxygen status within the hyperoxic zone. This method has multiple drawbacks such as limited information from

intermittent sampling to potential delay due to the time difference between blood draw and when the PaO2 value is obtained through blood gas machines, and potentially significant loss of blood due to multiple blood draws.

The Oxygen Reserve Index (ORi) is a reference that could help clinicians with their assessments of normoxic and hyperoxic states by scaling the measured absorption information between 0.00 and 1.00.

While not a direct measurement of PaO2, ORi provides a continuous and non-invasive index which correlates with changes in PaO2 values in the range of 100 to 200mmHg.

ORi together with pulse oximetry may provide useful reference information about a patient's partial pressure of oxygen in arterial blood (PaO2) and the transition between oxygen regions such as moving from normoxic to hypoxic regions. This can be useful during clinical applications such as during endotracheal intubation, in which unintended desaturations may occur. Additionally, ORi may be used as reference information for clinicians when they monitor the patient's reserve oxygen supply.

[figure not shown]

Figure 2: PaO2 vs SaO2 and SvO2

This protocol is designed to evaluate the correlations between  $\Delta ORi$  and  $\Delta PaO2$  and the potential use of ORi as an early warning of impending arterial oxygen desaturation.

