# 2.2 Hypothesis (constructed as the null):

Intraoperative changes in ORi will not correlate with increases in arterial oxygen content during pre-oxygenation or induction of general anesthesia and ORi will not provide clinically significant additional warning of impending arterial desaturation.

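### Pooled sensitivity in 8.3 includes a saturation-triggered sample that is an easy hit; it can describe agreement with PaO2 change but cannot support a claim of warning beyond SpO2

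*Combined protocol and SAP*

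**What the plan says.** Section 7 plans five paired ORi and blood gas measurements: baseline (sample 1), after pre-oxygenation (2), during stable mask ventilation just before laryngoscopy (3), on a saturation trigger (4), and five minutes into controlled ventilation on 100% oxygen (5). For sample 4, section 7.4 reads "When the arterial hemoglobin saturation reaches fourth ORi will be recorded"; the trigger value is redacted. Ventilation is then started or resumed.

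Section 8.3 defines sensitivity as N3/(N2 + N3), with a reference time that "is the sample time at the end of 100% pre-oxygenation". It adds that "all PaO2 samples for sick subjects are accounted for in data analysis", including samples outside 100 to 200 mmHg. No split by time point is planned. Section 8.2 sets the limit at more than 85% and presents the measure as ORi performance against PaO2 change.

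Section 1.1 says that ORi is scaled from 0.00 to 1.00, that it "correlates with changes in PaO2 values in the range of 100 to 200mmHg", and that "SpO2 is sensitive in the normoxic and hypoxic regions and largely remains flat in the hyperoxic region".

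Early warning is a specific aim (2.1) and the secondary endpoint (3.1). The null hypothesis in 2.2 includes that "ORi will not provide clinically significant additional warning of impending arterial desaturation". Section 8 contains no SpO2 comparator, no lead-time measure and no other analysis of that endpoint.

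**The concern.** The pairs that enter sensitivity are not equally demanding. Samples 3 and 5 are drawn at procedural time points. Sample 4 is drawn because saturation has reached a set value. If that value is a fallen saturation, section 1.1 implies that PaO2 has already left the hyperoxic region and that ORi should be at or near its floor. A hit at sample 4 is therefore likely, but it comes when saturation has itself signalled the event.

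A pooled figure above 85% could thus owe a good deal to sample 4. Because section 8 offers nothing else on early warning, that figure is the one most likely to be cited for it, and it does not bear on the question.

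**Working it through.** **Inputs from the documents.** Sensitivity limit above 85% (8.2). Reference at the end of pre-oxygenation and all samples kept (8.3). Saturation trigger for sample 4 (7.4). Minimum of 22 subjects and of 4 invasive measurements each, against five planned draws (8.1 and section 7). One earlier result in 8.2, from a cited study of 106 surgical patients: "decreasing ORI had 77.7% sensitivity and 76.7% specificity for detecting decreasing PaO2".

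The figure of 22 is carried over from a healthy-subject calculation that the document does not give, so it cannot be reproduced. Nothing below depends on how it was derived.

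**Inferred, not stated.** The trigger is a fallen saturation, because it comes before ventilation is started or resumed. N3 counts pairs in which both PaO2 and ORi fell and N2 those in which PaO2 fell and ORi did not, from the form of the ratio.

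**Step 1: how sample 4 scores.** If PaO2 at sample 4 is below its value at sample 2, the pair enters the denominator. It is a hit if ORi has also fallen, which requires ORi above 0 at sample 2.

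**Step 2: sensitivity needed elsewhere.** Let t be the proportion of subjects with a sample 4, s its hit rate, f the mean number of other PaO2 falls per subject (0 to 2), and p the sensitivity on those. Then

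pooled = (t·s + f·p)/(t + f), and a pooled 85% needs p = (0.85(t + f) − t·s)/f.

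| Assumption about sample 4 | f = 1 | f = 2 |
|---|---|---|
| Every subject, always a hit (t = 1, s = 1) | (1.70 − 1)/1 = 70% | (2.55 − 1)/2 = 77.5% |
| Half the subjects, always a hit (t = 0.5, s = 1) | (1.275 − 0.5)/1 = 77.5% | (2.125 − 0.5)/2 = 81.25% |
| Every subject, hit 90% of the time (t = 1, s = 0.9) | (1.70 − 0.9)/1 = 80% | (2.55 − 0.9)/2 = 82.5% |

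**Step 3: illustration with the cited 77.7%.** Assume this sensitivity at the other samples. With w = t/(t + f) as sample 4's share of the falls, pooled = w·s + (1 − w)·0.777.

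| w | s = 100% | s = 95% | s = 90% |
|---|---|---|---|
| 1/2 (sample 4 plus one other fall) | 88.9% | 86.4% | 83.9% |
| 1/3 (samples 3, 4 and 5 all falls) | 85.1% | 83.5% | 81.8% |
| 1/5 (half the subjects reach the trigger, f = 2) | 82.2% | 81.2% | 80.2% |

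**Step 4: chance of an observed value above 85%.** Take 22 subjects, a sample 4 in each, 77.7% elsewhere and, as a simplification, independent pairs (binomial).

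- Two other falls per subject: without sample 4, 38 of 44 are needed, chance 11%. With it, 57 of 66 are needed, chance 47%, 33% or 21% for s = 100%, 95% or 90%.
- One other fall per subject: without sample 4, 19 of 22 are needed, chance 24%. With it, 38 of 44 are needed, chance 80%, 61% or 42%.

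The direction is the same throughout, because s exceeds 77.7% in every case. The size varies widely.

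**The case against.** **The measure does not claim to show early warning.** Section 8.2 defines it against PaO2 change, and sample 4 is a genuine PaO2 fall. This stands: pooling is valid for that purpose. What remains is that section 8 has no analysis of the early-warning endpoint, so the pooled figure may be used in its place.

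**A reader might infer that sample 4 is a hit by construction.** The documents do not support that. The draw depends on saturation, not on ORi. If ORi was still 0 after pre-oxygenation, which is conceivable in an ASA III or IV population, it cannot fall and the pair is a miss. This is a matter of easy cases, not circularity.

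**A reader might also infer that sample 4 alone carries the criterion past 85%.** That needs it to be present in every subject as well as nearly always a hit. The minimum of four measurements against five draws allows it to be absent, and a subject intubated quickly may not reach the trigger. At a 90% hit rate with samples 3, 4 and 5 all falls, the illustration gives 81.8%, which fails.

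**SpO2 at sample 4 cannot simply be taken as 100% sensitive.** Section 7.4 refers to arterial hemoglobin saturation and does not name the monitor that supplies the trigger.

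**The split does not settle early warning.** Lead time concerns the interval before sample 4. At samples 3 and 5 PaO2 may exceed 200 mmHg, beyond the stated range of ORi. Both points stand and limit what the fix can show.

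**The reference time is itself unsettled.** Section 8.2 uses the sample closest to a PaO2 threshold; 8.3 uses the end of pre-oxygenation for sensitivity. This point rests on 8.3.

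**Conclusion.** The point holds as one of interpretation and reporting. Under the 8.3 reference, sample 4 is an easy case that tends to raise pooled sensitivity. The pooled figure remains a legitimate summary of agreement with PaO2 change, but neither it nor sample 4 alone can support the additional-warning hypothesis.

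The documents do not fix the size of the lift. Across the scenarios in step 2, the other samples need between 70% and 82.5% for a pooled 85%, instead of 85% on their own. This rests on the inferred meaning of the trigger and of N3, on the assumed presence and hit rate of sample 4, and on the 8.3 definition of t_ref. The trigger value, the PaO2 window, the range of ignored changes and Figure 3 are not visible and could alter the size. A change to the plan is worthwhile because it is cheap and limits what could be wrongly concluded.

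**What to change.** In 8.3:

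- Keep the pooled sensitivity, and also report it separately for sample 4 and for samples 3 and 5, with numerators, denominators and confidence intervals that allow for repeated samples per subject (for example, a bootstrap by subject).
- Beside each, score the change in SpO2 recorded by the same Radical-7, using the same N3/(N2 + N3) rule and the same reference sample.
- State that the pooled figure and sample 4 alone do not support a claim of warning beyond SpO2, and that misses at samples 3 and 5 with PaO2 above 200 mmHg may reflect the stated range of ORi.
- Reconcile the t_ref definitions in 8.2 and 8.3.

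This takes a few lines and one table, with no added sampling or subjects. The cost is smaller denominators: with 22 subjects, at most 22 pairs for sample 4 and 44 for samples 3 and 5, hence wide intervals. It does not replace a lead-time analysis, which the early-warning endpoint would still need.
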